8.8.1 Hydroxychloroquine Dose Modification

Any AE of \geq Grade 3 and attributed as possibly, probably or definitely related to HCQ will result in the dose being held until the AE has resolved to \leq grade 1 or baseline while EVE dosing may continue uninterrupted. If the AE resolves, reinstatement of treatment can occur but at a reduced dose as described in Table 9. If the AE recurs at the reduced dose, treatment will be held until the AE has resolved to \leq grade 1 and when resolved treatment can be reinstated at the next lower dose level. No more than 2 dose reductions are allowed during the maintenance cycles.

Table 9: Hydroxychloroquine Dose Reduction Schema

Dose Level	Dose mg/day	Reduce to
-2	400 mg twice daily	400 mg daily
-1	600 mg am and 400 mg pm	400 mg twice daily
1	600 mg twice daily	600 mg am and 400mg pm

If any AEs occur at grade \leq 2 that are attributed as possibly, probably or definitely related to HCQ, HCQ may be continued and the AE managed with supportive care, with the exception of visual field deficit. **Visual field deficit is a potential symptom of peripheral retinal toxicity should prompt drug discontinuation and ophthalmologic evaluation immediately. With particular regard to visual field deficits patients should be cautioned to report any visual symptoms, particularly difficulty seeing entire words or faces, intolerance to glare, decreased night vision, or loss of peripheral vision.**

If any AEs occur at grade \leq 2 that are attributed as possibly, probably or definitely related to HCQ, HCQ may be interrupted if the toxicity is either intolerable to the patient or PI/physician discretion determines it is in the best interest of the patient. In such cases, HCQ should be interrupted until recovery to grade \leq 1. If

resolution occurs in ≤ 7 days HCQ may be reintroduced at the same dose. If resolution takes > 7 days HCQ should be reintroduced at the lower dose level. If the event returns to grade 2, then HCQ should be interrupted until recovery to grade ≤ 1 , after which HCQ should be reintroduce at the lower dose level.

8.8.1.1 Management of suspected HCQ induced myopathy

Myopathy leading to muscle weakness is a rare but potentially serious side effect of HCQ. In our experience, this toxicity resolves with holding drug and can be reduced by reducing dose. With close attention to early signs of this toxicity, the goal is for it to be managed before it becomes serious and reaches a higher grade. Therefore, in the instance of grade >1 muscle weakness and/or elevated CPK or at MD discretion (even if the related AE is still only grade 1), HCQ should be held. When myopathy/muscle weakness returns to grade ≤ 1 (or after holding for a period per MD discretion, as long as symptoms and lab values are trending back to normal), HCQ may be reintroduced at the next lower dose level. It is not necessary that CPK return to grade ≤ 1 to restart drug, so long as myopathy has. It is intended that close monitoring and implementing HCQ dose reduction at early signs of myopathy will prevent subjects progressively worsening to the point that they have to come off study drug (HCQ) altogether.

8.8.2 Everolimus (EVE) Dose Reduction Guidelines

Known EVE hematological toxicities will not be attributed to HCQ but will only be attributed to EVE and will result in the following EVE dose modifications, as shown in Table 11. Hematologic toxicity of unexpected severity may be attributed to HCQ (in addition to EVE at investigator discretion). Non-hematological toxicities having an attribution to EVE of possible, probable or definite will result in the following EVE dose modifications, as shown in Table 11. For EVE dosing, the patient must have an ANC $\geq 1.0 \times 10^9/L$ and platelet count $> 75 \times 10^9/L$. All non-hematological toxicity grade ≥ 3 (except for alopecia, nausea and vomiting) must have resolved to CTCAE grade ≤ 1 . If toxicity persists, treatment should be delayed by one week for up to 4 consecutive weeks. If after 4 weeks (28 days) of delay all toxicity has still not resolved, any further treatment with EVE should be stopped. HCQ may be continued after EVE has been stopped on the combination arm.

Table 10: EVE Dose Reduction Guidelines

Dose Level	Dose	Reduce to
1	10 mg daily	5 mg daily
-1	5 mg daily	5 mg every other day
-2	5 mg every other day	Discontinue EVE

If any non-hematological toxicity observed Grade ≥ 3 (except for alopecia, nausea and vomiting) and/or if platelets $< 75 \times 10^9/L$ and/or ANC $< 1 \times 10^9/L$, causing delay of two weeks of EVE then the dose should be reduced by one dose level (see Table 10). For patients who would require dose >2 dose reductions EVE will be stopped. If any non-hematological toxicity observed was CTCAE **Grade 4** (except for alopecia, nausea and vomiting) then EVE should be **stopped**.

Table 11: Criteria for dose-modification for suspected EVE toxicity and re-initiation of EVE treatment

Toxicity	Actions
Non-hematological toxicity	
Grade 2 (except pneumonitis – refer to Table 6)	If the toxicity is tolerable to the patient, maintain the same dose. If the toxicity is intolerable to patient, interrupt EVE until recovery to grade ≤ 1 . If resolution occurs ≤ 7 days reintroduce EVE at same dose. If resolution takes > 7 days or if the event returns to grade 2, then interrupt EVE until recovery to grade ≤ 1 . Then reintroduce EVE at lower dose level.
Grade 3 (except hyperlipidemia*) (except pneumonitis – refer to Table 6) (except hypophosphatemia, refer to Section 8.6.8)	Interrupt EVE until recovery to grade ≤ 1 . Then reintroduce EVE at the lower dose level. For pneumonitis consider the use of a short course of corticosteroids.
Grade 4	Discontinue EVE
Hematological toxicity	
Grade 2 Thrombocytopenia ($<75,000 - 50,000/\text{mm}^3$; $<75 - 50.0 \times 10^9/\text{L}$)	Temporary dose interruption until recovery to Grade ≤ 1 . Re-initiate treatment at the same dose.
Grade 3 Thrombocytopenia ($<50,000 - 25,000/\text{mm}^3$; $<50.0 - 25.0 \times 10^9/\text{L}$)	Interrupt EVE until resolution to grade ≤ 1 Re-initiate treatment at a lower dose.
Grade 4 Thrombocytopenia ($<25,000/\text{mm}^3$; $<25.0 \times 10^9/\text{L}$)	Interrupt EVE until recovery to grade ≤ 1 . Then reintroduce Everolimus at one dose level lower, if available.
Grade 3 Neutropenia ($<1,000 - 500/\text{mm}^3$; $<1.0 - 0.5 \times 10^9/\text{L}$) or anemia	Temporary dose interruption until recovery to Grade ≤ 2 . Re-initiate treatment at the same dose
Grade 4 Neutropenia ($<500/\text{mm}^3$; $<0.5 \times 10^9/\text{L}$) or anemia	Interrupt EVE until recovery to grade ≤ 2 . Reintroduce EVE at one dose level lower, if available.**
Grade 3 Febrile Neutropenia (ANC $<1,000/\text{mm}^3$ with a single temperature of $> 38.3^\circ\text{C}$ (101°F) or a sustained temperature of $\geq 38^\circ\text{C}$ (100.4°F) for more than one hour)	Hold further dosing until Grade ≤ 2 ANC and no fever. Then resume dosing at the next lower dose level if available.
Grade 4 Febrile Neutropenia (life-threatening consequences ; urgent intervention indicated))	Discontinue EVE.
Recurrence of grade 3 toxicity after dose reduction	Reduce dose to the next lower dose level, if available. The lowest possible dose level of EVE is 5 mg every other day (2.5 mg daily). Below this level, EVE must be discontinued.
**Recurrence of grade 4 toxicity (including febrile neutropenia) after dose reduction	Discontinue EVE
**Any toxicity requiring interruption for > 28 days	Discontinue EVE

*Grade 3 hyperlipidemia (hypercholesterolemia and/or hypertriglyceridemia) should be managed using medical therapies.

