8.6.5 Management of hyperlipidemia and hyperglycemia

Treatment of hyperlipidemia should take into account the pre-treatment status and dietary habits. If blood lipid levels exceed the thresholds identified in eligibility

criterion 4.2.13 and treatment of hyperlipidemia is being considered, further blood tests to monitor hyperlipidemia must be taken in the fasting state.

Hypercholesterolemia (> 300 mg/dL or 7.75 mmol/L) or hypertriglyceridemia (>2.5 x ULN) should be treated with a 3-hydroxy-3-methyl-glutaryl (HMG)-CoA reductase inhibitor (e.g., atorvastatin, pravastatin) or appropriate lipid-lowering medication, in addition to diet. Patients should be monitored clinically and through serum biochemistry for the development of rhabdomyolysis and other adverse events as required in the product label/data sheets for HMG-CoA reductase inhibitors.

Note: Concomitant therapy with fibrates and an HMG-CoA reductase inhibitor is associated with an increased risk of a rare but serious skeletal muscle toxicity manifested by rhabdomyolysis, markedly elevated creatine kinase (CPK) levels and myoglobinuria, acute renal failure and sometimes death. The risk versus benefit of using this therapy should be determined for individual patients based on their risk of cardiovascular complications of hyperlipidemia.

Grade 3 **hyperglycemia** has been observed in patients receiving EVE therapy. In many cases in study EVE C2222, the affected patients had an abnormal fasting glucose at baseline. Based on this finding, it is suggested that optimal glucose control should be achieved before starting a patient on EVE and should be monitored during EVE therapy.

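### Section 8.8.2 and its Table 11 give different default everolimus actions for severe nausea/vomiting and grade 3 hyperlipidemia, and Table 11 sends pneumonitis to the wrong table

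*Protocol*

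**What the plan says.** Section 8.8.2 states, once for hematological and once for non-hematological toxicity, that an event attributed to EVE "will result in the following EVE dose modifications, as shown in Table 11". The running text then adds rules of its own:

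- **Condition for dosing.** All non-hematological toxicity of grade 3 or worse ("except for alopecia, nausea and vomiting) must have resolved to CTCAE grade" 1 or lower. If it has not resolved after 28 days of delay, "any further treatment with EVE should be stopped".
- **Reduction.** Toxicity of grade 3 or worse, with the same three exemptions, "causing delay of two weeks of EVE then the dose should be reduced by one dose level".
- **Grade 4.** EVE is to be stopped, again with the same three exemptions.

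Table 11 has a different list. Its grade 3 non-hematological row exempts hyperlipidemia, pneumonitis and hypophosphatemia. For everything else EVE is held until grade 1 or lower, and the action cell continues: "Then reintroduce EVE at the lower dose level. For pneumonitis consider the use of a short course of corticosteroids". Its grade 4 non-hematological row discontinues EVE with no exemption. Its footnote says that grade 3 hyperlipidemia "should be managed using medical therapies", and section 8.6.5 says that raised lipids "should be treated with a 3-hydroxy-3-methyl-glutaryl (HMG)-CoA reductase inhibitor" or another suitable lipid-lowering drug.

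For pneumonitis, the grade 2 and grade 3 rows of Table 11 refer the reader to Table 6. Table 6 (section 8.6.9.1) covers hepatitis B reactivation. Pneumonitis management is in Table 4 (section 8.6.6).

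**The concern.** A dose-modification section should give one default action for one event. Here two investigators who both follow section 8.8.2 can act differently. One continues EVE through grade 3 nausea in an Arm B patient, because the text exempts nausea. The other holds EVE and restarts it one level down, because Table 11 does not. At grade 4 the difference is between continuing EVE and stopping it. For grade 3 hyperlipidemia the direction reverses: the text holds EVE and stops it if the event has not resolved after 28 days, while Table 11 treats the lipids and leaves EVE alone.

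At stake are the safety of patients with potentially curable disease and uniform EVE dosing across patients. The pneumonitis pointer adds a smaller risk. Table 4 reduces EVE at grade 2, whereas the general grade 2 row of Table 11, if someone fell back on it, keeps the dose when the event is tolerable.

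**Working it through.** **Side-by-side reading**

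| Event attributed to EVE | Text of 8.8.2 | Table 11 |
|---|---|---|
| Grade 3 nausea/vomiting | Exempt from the hold and the two-week reduction | Hold to grade 1 or lower, restart one level down |
| Grade 4 nausea/vomiting | Exempt from the stop | Discontinue EVE |
| Grade 3 hyperlipidemia | Not exempt: must reach grade 1 or lower; reduced after a two-week delay; stopped if unresolved after 28 days | Exempt; medical therapy (footnote; also 8.6.5) |
| Grade 4 hyperlipidemia | Stop | Discontinue: no conflict |
| Grade 3 hypophosphatemia | Not exempt | Exempt; 8.6.8 settles it in words |
| Grade 2–3 pneumonitis | No separate rule | Referred to Table 6; should be Table 4 |

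Reading the text as merely additional to Table 11 does not remove the nausea/vomiting conflict, because the text's exemption would then have no effect. In combination patients Table 8 reduces HCQ first for nausea. Its lead-in also names vomiting, but the table has no vomiting row. Arm B takes no HCQ in cycles 1–6, so Table 8 cannot help there.

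**How many patients**

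Assumptions: 15 patients in Arm B; 45 on EVE in Arms B, C and D (15 + 30); event rates from the earlier HCQ/EVE renal-cell trial; each reported episode counted as one patient. The protocol summarizes that trial twice: 29 patients in section 3.8, and 34 patients in section 3.6 and its table. Expected number = rate × patients; intervals are Clopper-Pearson 95% limits × patients.

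*Section 3.8 summary (n = 29)*
- Grade 3 nausea, Arm B: 2/29 = 0.069; × 15 = 1.03 (0.13 to 3.41)
- Grade 3 triglycerides, EVE arms: 1/29 = 0.034; × 45 = 1.55 (0.04 to 7.99)
- Sum: 1.03 + 1.55 = 2.58, about 2.6

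*Section 3.6 summary (n = 34)*
- Grade 3–4 nausea or vomiting, Arm B: 0/34; × 15 = 0 (0 to 1.54)
- Grade 3–4 triglycerides, EVE arms: 2/34 = 0.059; × 45 = 2.65 (0.32 to 8.85)
- Sum: 0 + 2.65 = 2.65, about 2.6

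Vomiting in the 30 combination patients, where Table 8 has no row: 0/34 × 30 = 0 (0 to 3.08).

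Chance of at least one case = 1 − (1 − rate)^n. Triglycerides at 2/34 in 45 patients: 1 − (32/34)^45 = 0.94. Nausea at 2/29 in 15 patients: 1 − (27/29)^15 = 0.66; at 0/34 the estimate is zero.

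No pneumonitis rate can be given, because the earlier trial's table does not list it.

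**The case against.** The strongest reply is that the section is headed as guidelines, that only the resolution rule says must (the reduction and grade 4 rules say should), and that section 8.8 allows documented physician discretion. That stands: a reader might infer a set of binding, contradictory orders, and the documents do not support so strong a reading. But discretion is for departing from a default, and here there are two defaults.

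Second, hyperlipidemia is largely settled, since Table 11 exempts it by name and the footnote directs medical therapy. This also stands in good part. Neither the footnote nor 8.6.5 says in words that EVE continues, however, so the unqualified must in the text remains to be reconciled.

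Third, nausea/vomiting is a narrow case. That is right. Section 8.6.3 gives antiemetic care, Table 8 covers nausea in combination patients, and the only non-zero rate, 2/29, comes from patients who were also taking HCQ. Section 3.4 reports nausea as dose-limiting for HCQ at 800 and 1200 mg, so 2/29 probably overstates the rate on EVE alone.

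Three further inferences are tempting but not supported:

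- **Cytopenias.** The text's two-week reduction trigger for low platelets or neutrophils is missing from the Table 11 rows that say "Re-initiate treatment at the same dose". The two can coexist: same dose after a short hold, lower dose after a hold of two weeks. This is a gap in clarity, not a contradiction.
- **Pneumonitis time limits.** Table 4's limits of 3 weeks (grade 2) and 2 weeks (grade 3) do not clash with 28 days. They apply earlier, and Table 11 takes grade 2–3 pneumonitis out of its general rows. Sections 3.5.4 and 8.5.3 also point to the right place, so an investigator is unlikely to manage pneumonitis from a hepatitis table.
- **A range of 1.6 to 3.7 patients.** This arises only by taking nausea from one summary of the trial and triglycerides from the other. Kept within one summary, both totals are about 2.6.

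**Conclusion.** The plan is wrong as written on a narrow point. Section 8.8.2 and Table 11 give different default EVE actions for grade 3–4 nausea/vomiting, mainly in Arm B, and for grade 3 hyperlipidemia. The pneumonitis cross-reference is also wrong. The textual finding needs no assumption.

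The size does. About 2.6 patients rests on borrowed rates, on the nausea figure applying to EVE alone, and on 45 EVE-treated patients. The intervals run from near zero to about 9 for lipids alone. The 2/34 triglyceride figure pools grades 3 and 4, and only grade 3 creates a conflict. In the other direction, Arm A patients who add EVE after cycle 6 are not counted.

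A reader might infer that the primary result is at risk. It is not: a grade 3 or 4 event already counts against feasibility under section 12.2.1, whichever dosing rule follows. The gain is safer and more uniform EVE dosing, and the correction should be made.

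**What to change.** - State in 8.8.2 that Table 11 governs EVE dose changes.
- Delete nausea and vomiting from the text's exemptions, so that an EVE-attributed grade 3 event means hold and restart one level lower, and grade 4 stops EVE. In combination patients apply Table 8 first (HCQ reduced first), and add a vomiting row to Table 8.
- Add grade 3 hyperlipidemia to the text's exemptions, and hypophosphatemia with a pointer to 8.6.8.
- Change Table 6 to Table 4 in both pneumonitis entries of Table 11, and remove the pneumonitis sentence from the grade 3 action cell.
- Optional: say whether the two-week trigger applies to the same-dose cytopenia rows.

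The cost is protocol wording only. The one downside is slightly less EVE exposure in the few patients with severe nausea or vomiting on EVE alone.

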9 DRUG FORMULATION AND STORAGE

9.1 Agent #1: Hydroxychloroquine

Generic name: Hydroxychloroquine sulfate

Commercial name: Plaquenil

Chemical name: 7-Chloro-4-[4-[ethyl-(2-hydroxyethyl)amino]-1-methylbutylamino] quinolone

Hydroxychloroquine sulfate is a colorless crystalline solid, soluble in water to at least 20 percent; chemically the drug is 2-[[4-[(7-Chloro-4-quinolyl) amino]pentyl] ethylamino] ethanol sulfate (1:1).

9.1.1 Supply

As described above, hydroxychloroquine will be obtained through a written prescription by study MD as an initial 28- day supply and refilled every cycle. Patients will be required to bring the prescription to their visit on day 1 of each cycle, along with previous months' pill container so that pill counts can be performed. In addition, treatment diaries will be used to monitor adherence to therapy. Patients are required to bring the pill bottles and treatment diaries to each visit.

9.1.2 Formulation

PLAQUENIL (hydroxychloroquine sulfate) tablets contain 200 mg hydroxychloroquine

sulfate, equivalent to 155 mg base, and are for oral administration.

Inactive Ingredients: Dibasic Calcium Phosphate, Hydroxypropyl Methylcellulose, Magnesium Stearate, Polyethylene glycol 400, Polysorbate 80, Starch, Titanium Dioxide.

9.1.3 Dosing, Administration and Storage

When taking HCQ twice daily, the two daily doses should be taken 12 hours apart as close to 9am and 9pm as possible and documented clearly on the patient calendar. Patients receiving antacids, sucralfate, cholestyramine, and/or bicarbonate should have the HCQ drug dose administered at least 1 hour before or 2 hours after these medications. Missed doses should not be made up; patient should resume planned dose at next dosing interval.

9.2 Agent #2: Everolimus

Generic name: Everolimus

Commercial name: Afinitor™

Chemical name: dihydroxy-12-[(2*R*)-1-[(1*S*,3*R*,4*R*)-4-(2-hydroxyethoxy)-3-methoxycyclohexyl]propan-2-yl]-19,30-dimethoxy-15,17,21,23,29,35-hexamethyl-11,36-dioxa-4-azatricyclo[30.3.1.0^{4,9}]hexatriaconta-16,24,26,28-tetraene-2,3,10,14,20-pentone

9.2.1 Supply

Everolimus will be supplied by Novartis Pharmaceuticals Corporation for this trial and dispensed by the Oncologic Investigational Pharmacy at the Abramson Cancer Center of the University of Pennsylvania.

9.2.2 Formulation

EVE is formulated as tablets for oral administration of 5mg strength. Tablets are blister-packed under aluminum foil in units of 10 tablets, which should be opened only at the time of administration as drug is both hygroscopic and light-sensitive.

9.2.3 Dosing, Administration and Storage

Patients randomized to an EVE-containing arm will receive EVE as a dose of 10 mg orally daily, on a continuous basis. Patients will be instructed to take EVE in the morning, at the same time each day. EVE may be taken with or without food.

9.3 Drug Accountability

Clinical drug supply must be accounted for and patients will be asked to return all unused study drug and packaging on a regular basis, at the end of the study or at the time of study drug discontinuation. Accountability for the drug at all study sites is the responsibility of the principal investigator and designated Pharmacy representative. The investigator will ensure that the investigational drug is used only in accordance with this protocol. Drug accountability records indicating the drug's delivery date to the site, inventory at the site, use by each patient, and destruction/disposal per institutional policy will be maintained by the clinical site. Accountability records will include dates, quantities, lot numbers, expiration dates, and patient numbers.

At the conclusion of the study, and, as appropriate during the course of the study, the investigator will return all used and unused study drug, packaging, drug labels, and a copy of the completed drug accountability ledger to Novartis.

10 SAFETY ASSESSMENTS

10.1 Adverse Events Reporting Period

Patients will be evaluated for evidence of toxicity from the time of the first dose of HCQ/EVE to 30 days after last study drug or longer in the event of residual toxicity.

10.2 Definitions

Adverse Event: An adverse event (AE) is any symptom, sign, illness or

experience that develops or worsens in severity during the course of the study. Intercurrent illnesses or injuries should be regarded as adverse events. Abnormal results of diagnostic procedures are considered to be adverse events if the abnormality:

- .. results in study withdrawal
- .. is associated with a serious adverse event
- .. is associated with clinical signs or symptoms
- .. leads to additional treatment or to further diagnostic tests
- .. is considered by the investigator to be of clinical significance

Serious Adverse Event: A serious adverse event (SAE) is any adverse event, without regard to causality, that is life-threatening or that results in any of the following outcomes: death; in-patient hospitalization or prolongation of existing hospitalization; persistent or significant disability or incapacity; or a congenital anomaly or birth defect. Any other medical event that, in the medical judgment of the Principal Investigator, may jeopardize the subject or may require medical or surgical intervention to prevent one of the outcomes listed above is also considered an SAE. A planned medical or surgical procedure is not, in itself, an SAE. Also specifically excluded from this definition of SAE is any event judged by the Principal Investigator to represent progression of the malignancy under study, unless it results in death within the SAE Reporting Period.

Post-study Adverse Event: All unresolved adverse events should be followed by the investigator until the events are resolved, the patient is lost to follow-up, or the adverse event is otherwise explained. At the last scheduled visit, the investigator should instruct each patient to report any subsequent event(s) that the patient, or the patient's personal physician, believes might reasonably be related to participation in this study.

